12.1 Study Power and Sample Size

The specific sample size for this investigation is not based on the testing of a specific hypothesis with a degree of power to detect a difference. As such, a maximum of 15 subjects will be enrolled in the study with the intent of establishing baseline outcomes for this procedure.

12.2 Performance Analysis Cohorts

12.2.1 Intent to Treat Analysis

All subjects who enroll in the study and are treated with the *da Vinci*® robotic surgical system will be included in the Intent-to-Treat analysis. Subjects who terminate prior to completing the study will have their score set to their last available value for the visits after

they terminated from the study with missing data. No other special data handling algorithms will be used for imputing missing data.

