8 STUDY ENDPOINTS

8.1 Primary Safety Endpoint:

The primary safety endpoint is muscle flap failure.

8.2 Primary Efficacy Endpoint:

Latissimus dorsi muscle flap viability evaluated by clinical assessment and doppler examination at the end of the muscle harvest portion of the surgical procedure.

8.3 Secondary Endpoints:

1. Evaluation of donor site complications through 6 months post-procedure.
2. If the flap is for external use, interval viability with a Doppler proximally and distally will be checked at 3 months post-procedure.
3. If the flap is for pedicled, internal use over an implant, no additional evaluation will be possible unless planned or unplanned reoperation exposes the muscle, at which time a Doppler evaluation would be undertaken.
4. Conversion rate (i.e., completion of the latissimus dorsi harvest procedure with the *da Vinci*® *Robotic Surgical system* without converting to an open procedure).
5. The validated QuickDASH questionnaire to evaluate postoperative shoulder function as compared to preoperative QuickDASH shoulder function.
6. Postoperative pain assessed by validated visual analog scale (VAS).
7. Physical therapy assessment of range of motion and strength of the affected shoulder using the validated American Shoulder and Elbow Surgeons (ASES) assessment tool.
8. Length of stay and analgesic use to be compared to historical controls of the open procedure.

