9.6 Evaluation Tests

The disabilities of the arm, shoulder and hand (QuickDASH) questionnaire is a self-administered outcome instrument developed as a measure of self-rated upper extremity disabilities and symptoms (Appendix E). The QuickDASH consists of 11 items scored 0 (no difficulty) to 5 (unable/extreme) with 8 optional occupational questions. It has been validated for longitudinal construct and been rated effective as a post-surgery measurement tool.¹¹

The validity of VAS has been well studied for eliciting reproducible pain assessments^{12,13,14}. In pain research VAS are considered 'the gold standard' for pain assessments. Subjects report their level of pain through the scale. A copy of the VAS is located in Appendix F.

The functional evaluation of the shoulder uses the American Shoulder and Elbow Surgeons (ASES) method which is a standardized form for shoulder assessment¹⁷. The physical therapy assessment section includes range of motion and strength. While a comparison is regularly made between the operated versus non-operated shoulder, for this study, the subject will have an initial baseline test done preoperatively to compare with the postoperative evaluation. The measurement of active and passive range of motion and the manual muscle-testing will be performed on all subjects by a member of the Physical Therapy staff. Shoulder mobility is expressed in degrees with abduction, adduction, intra-rotation and extra-rotation measured both actively and passively. A sample of the range of motion and strength forms are located in Appendix G.

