11 STUDY PROCEDURES

11.1 Subject Screening and Baseline Evaluation (Visit 1)

Subjects will be recruited for this study from MD Anderson. All subjects requiring latissimus dorsi muscle harvest procedures in conjunction with breast, scalp, upper extremity, or lower extremity reconstruction procedures will be screened for eligibility. The Investigator or a member of the research team will review the subject's medical history for eligibility and inclusion into the study. If all inclusion criteria are met and no exclusion criteria are present, the Investigator will inform the subject about the purpose of the study and will obtain written informed consent. The background of the proposed study along with the benefits and risks will be explained to the subject and questions will be answered. The subject must sign an informed consent that has been approved by the MD Anderson Institutional Review Board (IRB). Failure to provide informed consent renders the subject ineligible for the study.

The Investigator or a member of the research team will record the subjects' medical history and demographic information on a case report form tool. Protocol specific data and adverse events will be entered into the MD Anderson REDCap™ database. The first assessment of adverse events will take place in the operating suite at the time of surgery

and will continue for 6 months following surgery. The medical history will include information about previous treatments to further ensure compliance with the inclusion and exclusion parameters. The Investigator will conduct a medical history review and a physical exam. A pre-anesthesia appointment will also be coordinated. The Investigator or a member of the research team and subject will also complete a QuickDASH questionnaire. The subject will also undergo a physical therapy assessment to test the range of motion and strength of the shoulder to be used as a baseline postoperatively. As standard of care for patients undergoing these procedures, a pregnancy test will be ordered by the Anesthesia Department for appropriate female patients. This visit may be completed within 30 days prior to treatment/surgery.

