11.3 Follow Up Evaluations (Visits 3-6)

Patients will be seen in the office for a visit within 0-2 weeks and then within 2-4 weeks after the surgical procedure. The next visit will be between 1-3 months after the procedure. The final visit will be between 3-6 months after the procedure. At these postoperative visits, incisions and drain sites will be checked and donor sites will be evaluated for adverse events. Additionally, pain assessments, the QuickDASH questionnaires, and the range of motion and strength tests will be administered. Drains will be removed as appropriate at approximately 2 to 3 weeks after the procedure.

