11.4 Schedule of Events

The protocol does not require any clinic visits other than those that are standard of care for patients undergoing robotic-assisted harvest of the latissimus dorsi muscles.

Study Events	Screening & Baseline Evaluation (Visit 1) ¹	Procedure / Treatment (Visit 2)	Post Op Follow Up (Visits 3-6) ^{2,3}
Eligibility Screening	X		
Secure Informed Consent	X		
Medical History and Physical Exam (to include BMI)	X		

Pre-Anesthesia Appointment (to include Urine Pregnancy Test - if appropriate per Anesthesia)	X		
Baseline QuickDASH Questionnaire	X		
Baseline Physical Therapy Assessment (to include testing range of motion and strength of the shoulder)	X		
Robotic-Assisted Latissimus Dorsi Flap Harvest Procedure & Non-robotic Reconstruction Procedure		X	
Flap Viability Assessment via Clinical and Doppler Examinations		X	
Adverse Event Assessment		X	X
Postoperative QuickDASH Questionnaire			X
Postoperative Physical Therapy Assessment (to include testing of range of motion and strength of the shoulder)			X
Patient Questionnaire of Pain via VAS			X
Drains Removed			X

¹ Occurs within 30 days prior to surgery.

² Visit 3 (occurs between 0-2 weeks), Visit 4 (occurs between 2-4 weeks), Visit 5 (occurs between 1-3 months)

³ Final Visit (occurs between 3-6 months)

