12 STATISTICAL ANALYSIS PLAN

This is a prospective, non-randomized, single-arm study designed to assess the safety and feasibility of the *da Vinci*® robotic surgical system in latissimus dorsi muscle flap harvest procedures. A maximum of 15 subjects requiring latissimus dorsi flap harvest procedures in conjunction with breast, scalp, upper extremity, or lower extremity reconstruction procedures will be enrolled at MD Anderson in Houston, Texas.

The muscle flap failure will be monitored using the Bayesian stopping boundaries calculated based on beta-binomial distribution. We will consider that the *da Vinci*® robotic surgical system is promising in latissimus dorsi flap harvest if the muscle flap failure rate is below 10%. With a sample size of 15 patients, the probability of observing at least one muscle flap failure is 79.4%. The prior probability of muscle flap failure is modeled by beta distribution (Beta (0.1, 0.9)). Denoting the probability of muscle flap failure by θ , and it is compared to fixed target of 10%. The following decision criterion will be applied: Stop if $\text{Prob}\{\theta > 0.10 \mid \text{data}\} > 0.75$.

Patients will be monitored by a cohort size of 5 according to the following stopping boundaries for muscle flap failure. The patient enrollment will be halted for this safety monitoring because the status of muscle flap failure can be obtained right after surgery.

Number of patients evaluated	Stop if \geq muscle flap failure observed
5	2-5
10	2-10
15	Always stop with this many patients

The operating characteristics are summarized in the following table (based on simulations from 10,000 trials).

True DLT Rate	Prob (stop the trial early)
0	0
0.05	0.0861
0.10	0.2639
0.15	0.4557
0.20	0.6242
0.25	0.7560
0.30	0.8507

The above stopping boundaries and operating characteristics are calculated using MultcLean (v.2.1.0) design software downloaded from <http://biostatistics.mdanderson.org/SoftwareDownload>.

The muscle flap failure rate and its 95% confidence interval (CI) will be calculated using the exact method. Other outcome data to be collected will include: pain assessment using a validated VAS, QuickDASH score, and physical therapy assessment.

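### The intent-to-treat carry-forward rule lets a preoperative score, or a week 0–2 score, stand as the 3–6 month result

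*Combined protocol and SAP*

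**What the plan says.** Section 12.2.1 places every enrolled subject treated with the robotic system in the intent-to-treat set; no postoperative assessment is needed to enter it. For early leavers the rule is: "Subjects who terminate prior to completing the study will have their score set to their last available value for the visits after" they left. The rest of the sentence adds no condition on which value qualifies, and the next sentence rules out any other imputation.

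The scores the rule would naturally cover are these:

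- **QuickDASH.** Secondary endpoint 5 (section 8.3) is defined as a comparison with baseline: "The validated QuickDASH questionnaire to evaluate postoperative shoulder function as compared to preoperative QuickDASH shoulder function". The schedule in section 11.4 lists a "Baseline QuickDASH Questionnaire" at Visit 1.
- **Range of motion and strength.** Section 9.6 says "the subject will have an initial baseline test done preoperatively to compare with the postoperative evaluation", and section 11.1 provides for a "physical therapy assessment to test the range of motion and strength of the shoulder to be used as a baseline postoperatively".
- **Pain.** In section 11.4 the "Patient Questionnaire of Pain via VAS" is marked only at the follow-up visits, so no preoperative VAS is scheduled.

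All three are collected at each follow-up visit. On timing, section 11.3 says "Patients will be seen in the office for a visit within 0-2 weeks and then within 2-4 weeks after the surgical procedure", followed by visits at 1–3 and 3–6 months.

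The rule in 12.2.1 speaks only of a score and names no instrument. Section 12 lists the outcomes as "pain assessment using a validated VAS, QuickDASH score, and physical therapy assessment", which attaches that word to QuickDASH, so QuickDASH is the clearest case. The per-protocol analysis (12.2.2) imputes nothing. No sensitivity analysis for missing scores is described.

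**The concern.** Endpoints 5 and 7 ask how the shoulder after surgery compares with the shoulder before it. If the only value on file is the preoperative one, the rule compares that value with itself and records no change, whatever happened to the subject. Section 10.1 names impaired range of motion as a known risk when the thoracodorsal nerve is sacrificed, so a zero produced by the rule could hide the harm these measures are there to show.

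The opposite error arises when a score taken within two weeks of surgery is reported as a late result. If subjects recover with time, late disability and pain are overstated.

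The sample size section (12.1) describes the study as providing reference outcomes for the procedure rather than testing a hypothesis. The descriptive summaries are therefore the product, and with at most 15 subjects each imputed value carries visible weight.

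**Working it through.** The plan gives no figure that depends on this rule, so there is nothing to reproduce. The check has two parts: what the rule carries, and how much it can shift a mean.

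**1. What is carried, by time of leaving** (12.2.1 read against 11.1, 11.3 and 11.4)

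| Subject leaves | QuickDASH, range of motion/strength | VAS pain | Later visits filled |
|---|---|---|---|
| After surgery, before Visit 3 | Preoperative value | Nothing to carry | 4 |
| Between Visits 3 and 4 | Week 0–2 value | Week 0–2 value | 3 |
| Between Visits 4 and 5 | Week 2–4 value | Week 2–4 value | 2 |
| Between Visits 5 and 6 | 1–3 month value | 1–3 month value | 1 |

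In the first row, change = baseline − baseline = 0 at every visit. In the second, taking 3 months as about 13 weeks, the carried score is at least 13 − 2 = 11 weeks old at the final visit. The last two rows are a smaller concern. Visits before termination use observed scores. The withdrawal visit in section 9.5 is a safety evaluation with no functional or pain score named, so it does not close the gap.

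**2. Weight of each leaver**

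For k leavers among n treated, shift in mean = (k/n) × (carried − true score).

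- n = 15 (the maximum): k/n = 6.7%, 13.3%, 20.0% for k = 1, 2, 3.
- n = 10 (enrollment stopped at the second safety look): 10%, 20%, 30%.

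**3. Preoperative value carried**

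If leavers would have had the same mean change D as the others, reported mean change = D × (n − k)/n.

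- n = 15: 93.3%, 86.7%, 80.0% of D for k = 1, 2, 3. With D = 15 points: 14, 13, 12.
- n = 10, D = 15: 13.5, 12.0, 10.5.

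**4. Week 0–2 value carried**

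Assume the early score is 15 to 30 points worse than the true final score on a 0–100 scale. For k = 1:

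- n = 15: 15/15 = 1.0 to 30/15 = 2.0 points too high.
- n = 10: 1.5 to 3.0 points too high.

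**5. Both directions from one set of assumptions**

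Assume n = 15, true late worsening of 10 points and week 0–2 worsening of 30. Baseline carried: 10 × (15 − k)/15. Week 0–2 carried: [10 × (15 − k) + 30k]/15.

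| k | Baseline carried | Week 0–2 carried | True |
|---|---|---|---|
| 1 | 9.33 | 11.33 | 10 |
| 2 | 8.67 | 12.67 | 10 |
| 3 | 8.00 | 14.00 | 10 |

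The errors can partly cancel. One subject carried 15 points too good and one carried 30 points too bad give a net shift of (30 − 15)/15 = 1.0 point.

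The values of k, the score differences and the 0–100 scale are assumptions. The documents give no dropout rate, mean or SD. The k/n fractions do not depend on the scale.

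**The case against.** - **The zero-change path is narrow.** It needs a subject who has had surgery and then leaves before any postoperative scoring, that is, within about two weeks. Drain removal at roughly 2 to 3 weeks, and visits that are standard of care anyway, make this unlikely. This stands as a point about frequency. It does not make the rule give a sensible value when the case occurs.
- **The plan never says it will report means.** Section 12 lists these outcomes as data to be collected and specifies no summary statistic. A median or a subject listing would respond differently. This stands: the size estimates assume a mean. The false zero for the individual subject does not depend on that assumption.
- **The term score is undefined.** Range of motion is expressed in degrees and may not be meant. This stands in part: the concern is firmest for QuickDASH, and the ambiguity itself needs resolving.
- **Carrying a postoperative value is a declared method in an unpowered pilot, beside an unimputed per-protocol analysis.** It is fair to call the early-score case partly a matter of choice, and the per-protocol result does show completers without imputation. But that set keeps only subjects who completed according to protocol. It drops leavers' genuine early scores, and completers with deviations.
- **Functional harm is also recorded elsewhere,** through adverse events (11.1) and the functional-deficit summaries in section 12. True, and this limits the consequence.

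**Conclusion.** The concern holds and is minor. Followed as written, 12.2.1 assigns a change of exactly 0 to a treated subject who leaves before Visit 3, on endpoints defined as change from before surgery. It also lets a week 0–2 score stand for 3–6 months. The reading rests on the text alone. The size rests on assumed dropout, assumed score differences and a mean-based summary: 6.7% of the carried-minus-true gap per leaver at 15 subjects, 10% at 10. The net direction cannot be predicted.

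Only secondary endpoints 5–7 are affected, and only at visits after termination. Flap failure, flap viability at harvest and the stopping rule are untouched.

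**What to change.** Amend section 12.2.1 to:

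1. state that a preoperative value is never carried into a postoperative visit;
2. make the main intent-to-treat summary of QuickDASH, VAS and range of motion/strength the observed scores at each visit, with numbers observed and missing, and with change from baseline where a baseline exists (so not for VAS);
3. keep carry-forward of postoperative values as a sensitivity analysis only, and name the scores it covers.

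This is SAP wording; it needs no extra visits or data. The cost is fewer subjects at late visits, and observed-score summaries assume that those who left resemble those who stayed. The missing counts and the retained sensitivity analysis let the reader judge that assumption.

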12.2.2 Per Protocol Analysis

All subjects who complete the study according to the protocol will be included in the Per-Protocol analysis. No special data handling algorithms will be used for imputing missing data for subjects included in the Per-Protocol analysis.

12.3 Endpoint Analysis and Reporting of Results

All statistical analysis will be performed using SAS Version 9.3 (SAS Institute Inc., Cary, NC).

13 ADVERSE EVENT REPORTING

Adverse Event

An Adverse Event (AE) is any untoward medical occurrence, unintended disease or injury, or untoward clinical signs (including abnormal laboratory findings) in subjects, users or other persons, whether or not related to the investigational medical device. Note: This also includes events related to the study device and/or the study procedure. The U.S. Department of Health and Human Services, National Institutes of Health, National Cancer Institute, Common Terminology Criteria for Adverse Events (CTCAE), Version 4.03, will be used to grade adverse events.

All AEs related to the surgery that are observed by the Investigator or staff during a procedure, physical or laboratory examination, or mentioned by the subject either spontaneously or upon questioning will be recorded in REDCap™. Information pertaining to the recorded AE will be reviewed and verified by the IRB or its designated representative. The Investigator is responsible for assessing the severity of the AE, the causal relationship between any events and the clinical study procedure, activities or device. Additionally, the Investigator is responsible for providing appropriate treatment for the event and for adequately following the event until resolution. The following categories of adverse event severity are to be used by the Investigator:

- Mild: Awareness of a sign or symptom that does not interfere with the subject's usual activity or is transient, resolved without treatment and with no clinical sequelae;
- Moderate: Interferes with the subject's usual activity; and,
- Severe: Any fatal or immediately life-threatening clinical experience that requires a subject to be hospitalized, or hospitalization is unduly prolonged because of a

potential disability or danger to life or because an intervention has been necessitated. This includes any permanently disabling event.

The following categories of AE relatedness to the study device and procedure will be used by the Investigator:

- Possibly Related – may be related to study agent/device.
- Probably Related – is likely related to study agent/device.
- Definitely Related – is clearly related to study agent/device.

Adverse Device Effect (ADE)

An Adverse Device Effect (ADE) is defined as an adverse event related to the use of an investigational medical device. Note: This definition includes adverse events resulting from insufficient or inadequate instructions of use, deployment, installation, operation or any deficiency of the investigational medical device.

Serious Adverse Event (SAE)

The following events (including laboratory results and outcome events) will be considered SAEs and must immediately (within 1 working day [24 hours] from the time the research team becomes aware of the event) be reported to the IRB as set forth in the MD Anderson AE Policy (Chapter 15 of the Human Subject Research Manual). These events must be reported whether or not the Investigator believes they are related to the study procedures or the device.

A serious adverse event is any adverse event that:

- results in death;
- is life-threatening, (places the subject at immediate risk of death from the event as it occurred);
- results in inpatient hospitalization or prolongation of existing hospitalization;
- results in persistent or significant incapacity or substantial disruption of a person's ability to conduct normal life functions;
- results in a congenital anomaly/birth defect; or
- based upon appropriate medical judgment, may jeopardize the subject's health and may require medical or surgical intervention to prevent one of the other outcomes listed in this definition.

Serious Adverse Device Effect (SADE)

An adverse device effect that has resulted in any of the consequences of a serious adverse event. This includes SADE's which by its nature, incidence, severity or outcome

has not been identified for the investigational study device. SADE's must be reported to Intuitive Surgical within 24 hours by telephone, fax and/or email.

Unanticipated Serious Adverse Device Effect (USADE)

This includes SADE's which by its nature, incidence, severity or outcome has not been identified for the investigational study device. USADE's must be reported to the IRB in accordance with Chapter 15 of MD Anderson's IRB Policy on Adverse Event Reporting and Management.

Unanticipated Adverse Device Effect (UADE)

Any serious adverse effect on health or safety or any life-threatening problem or death caused by, or associated with, a device, if that effect or problem, was not previously identified in nature, severity, or degree of incidence in the investigational plan or application (including a supplementary plan or application), or any other unanticipated serious problem associated with a device that relates to the rights, safety, or welfare of subjects (21 CFR 812.3(s)).

Because no investigational drugs or regimens are used in this study, only Unanticipated Adverse Device Effects will be reported to the IRB and the IND Office. Events that are related to the neoadjuvant therapy or surgery will not be reported or recorded in the case report form.

All UADE will be reported to the IRB in accordance with the timeframes and procedures outlined in "The University of Texas M. D. Anderson Cancer Center Institutional Review Board Policy for Investigators on Reporting Unanticipated Adverse Events for Drugs and Devices".

Unless otherwise noted, the electronic SAE application (eSAE) will be utilized for safety reporting to the IND Office and IRB. Unanticipated Adverse Device Effects will be forwarded to FDA by the IND Sponsor (Safety Project Manager IND Office) according to 21 CFR 812.150.

It is the responsibility of the PI and the research team to ensure unanticipated adverse device effects are reported according to the Code of Federal Regulations, Good Clinical Practices, the protocol guidelines, the MD Anderson guidelines, and Institutional Review Board policy.

Device failure

Device failures which occur at the time of participant evaluation and which may prevent a participant from receiving therapy on trial will be kept on a log and will be reported as part of the annual report. Device failures at this point are not expected to affect patient safety, as participants may still receive appropriate therapy as determined by their attending physician.

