Patient information including age, gender, body mass index (BMI), medical history, history of radiation, history of smoking, defect characteristics (such as "partial breast, scalp, upper extremity, or lower extremity"), donor site morbidity, and functional deficits will be summarized. The rate of donor site morbidity and their 95% confidence interval will be reported.

Operative Variables: Length of surgery, type of defect, size of defect, type of reconstruction, length of incision used, length of robotic portion of the procedure, robotic instrumentation used, port placement. This information will be documented by the OR staff during surgery, and collected by the research team after surgery on standardized CRFs.

Outcome Variables: Length of stay, pain medication requirements, postoperative complications (such as seroma, wound dehiscence, delayed wound healing, or flap loss), length of time drains are required in donor site, and postoperative return to normal function, as well as, any residual functional deficits, defined as a subjective decrease in strength, range of motion or restriction in activities of daily living will be assessed at

between week 0-2, and between week 2-4 after the procedure. The subject will then have an evaluation at 3 months after the procedure. The subject's last follow up visit will occur 6 months post-procedure.

The safety of the robotic-assisted latissimus dorsi procedure will also be evaluated based on adverse events related to the donor site through 6 months post-procedure. Acute complications include but are not limited to: seroma; hematoma; overlying skin damage; and, injury to the muscle or vascular pedicle. All adverse events will be further categorized and documented according to section 13 of this clinical protocol.

The feasibility of the procedure will be evaluated based on the number of successfully completed robotic-assisted latissimus dorsi harvest procedures among the total attempted procedures. Any procedure that is abandoned or converted to an open surgical or endoscopic technique after being initiated with the *da Vinci*® robotic surgical system will be considered a failed *da Vinci*® procedure. The rate of successfully completed harvest procedure will be calculated along with its 95% CI.

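### Section 13's relatedness scale has no not-related level and merges device with procedure, so unrelated or procedure-only events cannot be coded as such; separately, two severity scales are required with no mapping

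*Combined protocol and SAP*

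**What the plan says.** **Relatedness.** Section 13, under Adverse Event, introduces the scale with "The following categories of AE relatedness to the study device and procedure will be used by the Investigator". It lists three levels: Possibly Related ("may be related to study agent/device"), Probably Related ("is likely related to study agent/device") and Definitely Related ("is clearly related to study agent/device"). No other level appears in the section.

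**Events the scale must serve.** The adverse event definition covers occurrences irrespective of any relation to the device. The investigator must judge causality against the procedure, study activities or the device. For serious adverse events the section adds: "These events must be reported whether or not the Investigator believes they are related to the study procedures or the device".

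**Device effects.** An ADE "is defined as an adverse event related to the use of an investigational medical device". No relatedness level is given as the cut-off. A SADE is an ADE with a serious outcome and goes to the manufacturer within 24 hours. UADEs go to the IRB, the IND Office and FDA.

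**Recording.** The Adverse Event text says that surgery-related events are entered in REDCap. The UADE text says that events related to surgery or neoadjuvant therapy are neither reported nor entered in the case report form.

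**Severity.** Events are to be graded by CTCAE v4.03. The next paragraph adds: "The following categories of adverse event severity are to be used by the Investigator", followed by Mild, Moderate and Severe.

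**Link to the analysis.** Section 12 states: "All adverse events will be further categorized and documented according to section 13 of this clinical protocol".

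**The concern.** A causality scale has to be able to return the answer no. This one cannot, although the definitions around it assume that some events will be unrelated. It also puts two questions into one field: was it the robot, and was it the operation?

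That second distinction is central to this trial. Sections 2 and 12 say that only the robotic harvest is under study, not the manual reconstruction, but both take place at the same visit (Section 11.4). An event from the reconstruction, or one that any latissimus harvest could cause, needs a code that does not point to the device.

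At stake are the classification of events as device effects, the expedited reports that follow from it, and how far the safety summary of a first formal evaluation can be read as evidence about the robot.

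**Working it through.** No arithmetic is involved in the defect and Section 13 states no figure to reproduce. The check sets the texts side by side.

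1. **Levels offered against judgements expected.** The scale has 3 levels, and 0 of them are not related or unlikely. The adverse event definition and the serious adverse event rule both allow for an unrelated judgement. The judgement is expected, but there is no code for it.

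2. **Heading against wording of the levels.** The introductory line speaks of device and procedure. Each of the three levels speaks only of the agent or device. An event caused by the operation but not by the robot fits the heading and none of the levels.

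3. **Does the protocol itself expect such events?** Yes.
   - Section 10.1 lists ten standard risks that it attributes to any latissimus harvest, whatever the technique, and describes endoscopic and robotic risks separately.
   - In the 52-patient endoscopic series in Section 3.2, 4 patients had skin flap necrosis in the reconstruction part and none had donor-site necrosis from the harvest.
   - In the sponsor's own 15 patients (Section 4.2), the one harvest complication, a nerve palsy, was put down to patient positioning.

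   The Section 13 scale could not record any of these distinctions.

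4. **What depends on the coding.** ADE, SADE and UADE status all turn on relation to the device, and so do the reports to the manufacturer, the IRB, the IND Office and FDA. The number of stated rules linking a relatedness level to ADE status is 0.

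5. **What does not depend on it.** Flap failure has its own Doppler-based definition, limited to 72 hours after surgery (Section 14.7), and the stopping rule counts only flap failures. Section 12 reports donor-site morbidity with a 95% confidence interval, without conditioning on relatedness. It plans no ADE rate and no table by relatedness or severity.

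6. **Granularity only.** If a subject-level device-effect rate were reported, one misattributed subject among the maximum of 15 would move it by 1/15 = 6.7 percentage points. This is the step size, not an estimate of the error.

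7. **Severity.** Two scales are mandatory, with 0 mapping rules and 0 statements of which one is analysed. Within the three-level scale, a transient event that interferes with usual activity, resolves untreated and leaves no sequelae meets both Mild and Moderate. Severe is built from death, threat to life, hospitalization and permanent disability, which largely repeats the serious adverse event criteria in the same section. Severity grading has no bearing on device attribution, so this is a second defect and does not aggravate the first.

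**The case against.** The best defence has five parts.

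- **Filtering before the scale.** Only surgery-related adverse events are recorded, so most unrelated events never reach the scale. This stands in part. It does not help with events related to the surgery but not to the robot, or with serious events, which are reported regardless of relation.
- **No analysis uses relatedness.** This is correct for the planned estimates, and it limits the point to event classification, reporting and the descriptive safety account. Section 12 nevertheless sends all adverse events to Section 13 for categorization.
- **The direction is not established.** This stands. If surgery-related events are kept out of the case report form, as the UADE text says, counts could be too low. The two recording statements conflict, so inflation cannot be asserted as the net effect.
- **The case report form may offer a not-related option.** Appendix H is not in the reviewed text, so this is possible. The form would then contradict Section 13, which would still need correcting.
- **Fine-grained attribution is excessive for 15 subjects.** This is fair. One not-related level and a split between device and procedure are enough.

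A reader might go further and infer that every recorded event becomes a device effect, so that the ADE rate equals the adverse event rate and every serious event is a SADE. The documents do not support this. No rule makes Possibly Related sufficient for an ADE, and nothing compels the investigator to force an event into a level that does not fit. The level could be left blank. Nor do the documents support saying that the trial's safety conclusion would be wrong, since the primary safety endpoint does not use the scale.

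**Conclusion.** The point holds in limited form. The relatedness rule is faulty as stated: it cannot express an unrelated or procedure-only event, although the surrounding definitions expect unrelated events and the protocol itself separates the harvest from the reconstruction. Device effects may be over-attributed to the robot or left unclassified. The documents give no share of unrelated or procedure-only events, so no size can be stated.

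The unmapped severity scales are a separate and real defect. A level-by-level conflict with CTCAE cannot be shown, because its grades are not reproduced in the documents.

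The conclusion assumes that investigators follow Section 13 as written and that the unseen case report forms do not already add the missing option. It should be corrected, but it does not threaten the primary safety endpoint.

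**What to change.** Amend Section 13 and the matching case report form fields:

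1. Add a not-related level, and an unlikely level if wanted.
2. Record relation to the robotic device in one field and relation to the procedure in another, with the harvest distinguishable from the mastectomy or reconstruction. Drop the word agent, since no drug is studied.
3. State which levels of the device field make an event an ADE, and hence a SADE or UADE.
4. Name CTCAE v4.03 as the only severity scale and delete the three-level list. Keep seriousness as a separate yes/no field.
5. Reconcile the statement that surgery-related adverse events are recorded with the statement that surgery-related events are neither reported nor recorded. Until this is done, no adverse event count has a clear scope.

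The cost is Section 13 wording and a few form fields, completed for at most 15 subjects. Events already coded on the old scale, if any, would need to be rated again. The sample size, endpoints and stopping rule do not change.
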